#### *Evaluation and statistical analysis*

Primary outcome is the mean CSQ-8 score for patients completing this post-intervention questionnaire. Secondary outcomes that concern clinically significant improvement are based on the algorithm for reliable change as specified by Jacobson and Truax (20), combined with the established cut-offs for anxiety and depression of 8 points on the GAD-7 and 10 points on the PHQ-9 (27). Clinically significant improvement is calculated based on the last observation from each patient. Dose-response relationships and change over time are analysed using linear mixed models, if deemed suitable for the data. Linear regression is used for other continuous outcomes, and chi tests for nominal data. Within-group effect sizes are presented in terms of Cohen's *d*, and standardised effect sizes are compared to British reference data (12).

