At inclusion and during the course, participants are encouraged to contact clinicians working with the group intervention if symptoms deteriorate. Each week, participants rate their mood including suicidal ideation using validated instruments. Their responses are reviewed by researchers in the project, and participants who experience a substantial deterioration in symptoms are contacted for a discussion about their further participation in the course. Participants also have the opportunity to contact their course leader via the study web page, via a secure system reminiscent of email. If necessary, the intervention is terminated and the participant is referred to routine care services.

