### *Measurements and psychometric instruments*

Assessments in the study are: the screening (for the eligibility interview), the pre-intervention assessment, five weekly measurements during the course (w. 1-5) and the post-intervention assessment. A follow-up assessment will also take place after 3 months. Thus, in total, there are 9 assessment points. The measurements are conducted using online questionnaires that are stored in the patient's digital record.

At the pre-intervention assessment, information is also collected during the eligibility interview. This interview involves questions about sociodemographic variables, a structured questionnaire for the assessment of suicidal ideation and severe psychiatric problems and questions concerning medication.

[Translated from the original that was approved by the Swedish ethical review authority]

At each group session, the participation of each patient is registered. Post intervention, the patient also meets with a clinician of the psychosocial team. This appointment is booked 6 weeks from the planned start of the course. This assessment is conducted in a manner analogous to routine care assessment by the psychosocial team of the primary care clinic. During this assessment, all further necessary arrangements are registered (e.g., no need for further arrangements, referral to psychiatric services or additional help and if so of what kind). The patient also reports on adverse events, satisfaction with the course, changes to medication and other therapies. Lifestyle behaviours are surveyed over the course of the study because little is known about lifestyle behaviours in Swedish primary care patients, and the relation between lifestyle behaviours and mental health has been identified by the Swedish national board of health and welfare as a high-priority topic in primary care research.

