Suicidal ideation is monitored during the course of the study. Each week, patients rate how much they are bothered by "thoughts that [they] would be better off dead, or of hurting [themselves]". Patients who score higher than "not at all" are contacted for an individual assessment, and are offered additional support and/or are referred to specialist care in accordance with common practice and routine care guidelines. Each week, patients are also tasked with answering an open-ended question about adverse events. Adverse events are highlighted in the system for data collection and prompt subsequent review. In addition, all patients' week-by-week change in mood is continuously reviewed, as is done in routine care for example at the Internet psychiatry unit of Region Stockholm.

In addition to questions about sociodemographic variables (such as age, sex, educational attainment, income and civil status), the following questionnaires are administered via the internet (the CSQ-8 in paper form [Note: All were administered online due to the covid-19 pandemic, see "Data safety and management" below.]):

Questionnaire	Outcome	Ref	SN	PRE	W	POST	3MFU
Client satisfaction questionnaire (CSQ-8)	Satisfaction with the course	(21)				x	
Generalised Anxiety Disorder 7-item Scale (GAD-7)	Anxiety	(22)	x	x	x	x	x
Patient Health Questionnaire 9 (PHQ-9)	Depression	(23)	x	x	x	x	x
Perceived Stress Scale 10 (PSS)	Stress	(24)		x		x	
12-item WHO Disability Assessment Schedule 2.0 (WHODAS 2.0)	Functional impairment	(25)		x		x	
Lifestyle behaviours	Lifestyle behaviours (tobacco, alcohol, physical activity, diet)	(26)		x		x	x

3MFU = 3-months follow-up, POST = post-intervention, PRE = pre-intervention, SN = screening, W = weekly during the course

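### Does the dose-response analysis need a prescribed time order and symptom adjustment because the course can be ended after deterioration?

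*Combined protocol and SAP*

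**What the plan says.** On dose-response, the Evaluation and statistical analysis section has one sentence: "Dose-response relationships and change over time are analysed using linear mixed models, if deemed suitable for the data". It names no dose variable, no order of exposure and outcome, and no covariates.

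Other sections supply the ingredients:

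- **Attendance.** The study aims list the number of lectures attended (six are given) as an exploratory measure of adherence. They do not call it the dose. Under Measurements and psychometric instruments, "At each group session, the participation of each patient is registered".
- **Symptoms.** GAD-7 and PHQ-9 are rated at screening, pre-intervention, weeks 1 to 5, post-intervention and three months. The text does not say whether a weekly rating comes before or after that week's lecture, or whether ratings go on once a patient's course has ended.
- **Stopping.** Under Intervention, "participants who experience a substantial deterioration in symptoms are contacted for a discussion about their further participation in the course", and "If necessary, the intervention is terminated and the participant is referred to routine care services". No threshold or expected frequency is given.
- **Other care.** Patients who endorse the weekly item on suicidal thoughts "are offered additional support and/or are referred to specialist care". At the post-intervention visit, "The patient also reports on adverse events, satisfaction with the course, changes to medication and other therapies".

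**The concern.** The ratings that trigger review include the symptom outcomes themselves, and every patient's "week-by-week change in mood is continuously reviewed". Worsening can therefore shorten a patient's course. If total lectures is then regressed against symptom change, patients who worsened have low counts because they worsened, and the slope suggests that more lectures help even when they do nothing. Adjusting for the baseline score does not remove this, because the stopping depends on what happens after baseline. With one group and non-randomised attendance, the design offers no other protection. The risk is that a gradient partly produced by who was stopped is read as evidence of benefit and carried into planning of the controlled trial mentioned under Significance.

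**Working it through.** **The plan's own figure.** No figure is attached to the dose-response analysis. The sample size under Design and power reproduces: a two-sided paired t-test at 0.05 with 80% power and d = 0.45 needs n = 40.72, and 40.72/(1 - 0.40) = 67.9, i.e. 68. It was set for pre-post change, not for dose.

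**Two readings of the dose.** Let A_ik = 1 if patient i attended lecture k, and let t run from PRE to POST.

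1. Total dose, D_i = sum of A_ik over all six lectures: y_ij = b0 + b1 t_j + b2 D_i + b3 t_j D_i + u0_i + u1_i t_j + e_ij. With t scaled 0 to 1, b3 is points of pre-post change per lecture.
2. Dose to date, C_ij = sum of A_ik over lectures before rating j: y_ij = b0 + b1 t_j + b2 C_ij + u0_i + u1_i t_j + e_ij.

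Both are linear mixed models, and both fit the plan's sentence. Under reading 1, D_i contains attendance that was decided after the earlier ratings and partly by them. Under reading 2, each C_ij depends only on the past. If stopping depends on recorded ratings, the joint likelihood factors into (rating given the past) x (attendance given the past). The second factor carries no information on b2, so maximum likelihood is not distorted by the stopping.

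**Simulation under zero lecture effect.** All inputs except n and the overall 40% loss are assumptions:

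- n = 68; baseline N(12, SD 4); individual linear change N(-2, SD 4); measurement SD 1.8
- 6% random weekly stopping; 10% randomly missed lectures
- POST missing 38-40% overall
- symptom-related stopping with weekly probability 25% or 50% once the latest rating is 5 (or 7) points above PRE
- 4,000 trials per scenario

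| Scenario | Terminated | Reading 1 slope | Rejection at 5% |
|---|---|---|---|
| No symptom-related stopping | 0 | 0.00 | 5.7% |
| 7 points, 25% | 0.7% | -0.06 | 6.0% |
| 5 points, 25% | 2.8% (0.028 x 68 = 1.9) | -0.17 | 9.0% |
| 5 points, 50% | 5.2% (0.052 x 68 = 3.5) | -0.31 | 16.1% |

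The 9.0% is distinguishable from 5.7%: the Monte Carlo standard errors are sqrt(0.09 x 0.91/4000) = 0.45 and sqrt(0.057 x 0.943/4000) = 0.37 percentage points, so z = 3.3/0.58 = 5.7. The 6.0% is not.

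Reading 1 moves with further assumptions:

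- If ratings cease when the course ends, the two 5-point slopes become -0.25 and -0.44.
- If care after stopping helps by 1.8 points per week, they shrink to -0.06 and -0.09 (rejection 6.7% and 7.5%).
- Under a different set of variances, absence rates and thresholds, with 2.5% to 17% terminated, the corresponding mixed-model term is -0.08 to -0.42 per lecture.
- With larger symptom variance and only 5% background absence, a change-score slope reaches -0.4 to -2.1.

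**Reading 2.** With random intercept and slope, weekly ratings and dose to date, the slope is 0.00 and rejection 4-5% in the scenarios run, with variance components set to their simulated values. The standard error is 0.24-0.27, so the 95% half-width is 1.96 x 0.24 = 0.47 to 1.96 x 0.27 = 0.53.

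**A lagged alternative.** Relating attendance at each lecture to the next rating, adjusted for PRE, the two latest earlier ratings and week, also gives about zero (-0.01 to 0.00). Its standard error is 0.41-0.46 (half-width 0.80 to 0.90), and it estimates only a one-week effect. With the assumed later care it gives +0.04 and +0.07. If the rating taken before a lecture is mistaken for its outcome, it gives -0.19 and -0.38.

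**The case for a change.** The strongest case for a change is that the plan commits to a dose-response analysis and leaves open exactly what decides its meaning. The only attendance count it defines is the total, so an analyst in a hurry may well use it. The route from worsening to fewer lectures is written into the protocol, and simulations under differing assumptions agree on its direction. A note on rating times and a caution about total attendance would cost only a few words.

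Much of this stands. The mechanism is real under reading 1, and the dose and rating times are undefined. Three things weaken the case for action.

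- Silence is not a choice of the biased model. The plan names mixed models in the same sentence as change over time, and it collects attendance per session and symptoms weekly, which is what reading 2 needs.
- The direction is less certain in practice than under the stopping rule alone. The documents also provide referral and extra support, which work against the false gradient, and early improvers may stop attending.
- A prescribed lagged model would be less precise than the ordinary one and would not answer a cumulative question. Its half-width of 0.80 to 0.90 exceeds the largest bias in the main set of scenarios (-0.44).

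The timing point applies to any time-ordered analysis, but the order of ratings and lectures should be known to the team that runs the course.

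**Conclusion.** No change to the plan follows. The text leaves out a detail that a competent analyst fills from data already collected: lectures attended before each rating, in the mixed model already named. Filled that way, the stopping rule produces no bias in the scenarios run. This rests on stopping depending on recorded ratings, on the random-effects structure being about right, and on the analyst knowing whether each rating came before or after the lecture.

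If a slope on total attendance were reported instead, it would be an association only. Its false component could be negligible (-0.06) or material (-0.31 to -0.44, more under other assumptions), and the documents do not allow a choice between these. The consequence is limited either way. Dose-response appears in no hypothesis or listed outcome, the analysis is conditional on suitability, and neither the CSQ-8 primary outcome, the clinically-significant-improvement criteria nor the sample size depends on it. Tests of effect against a control are left to a later trial.

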### ***Research question (study aims)***

The aim of this within-group study is to evaluate a CBT-based intervention similar to SC, focusing on feasibility and efficacy in Swedish primary care, with British reference data (12). The study includes a combination of patients with clinically significant levels of anxiety or depression and patients with subclinical symptoms, analyses concerning the clinical group being the primary focus of the study. The primary outcome is patient satisfaction, see below. Secondary outcomes include adherence to the protocol and effects on psychiatric symptoms in terms of anxiety and depression. Perceived stress, functional impairment and adverse events are also surveyed to make it possible to assess the relevance of the intervention for stress-related mental health problems, enable comparisons versus other protocols and ensure that the intervention is safe and does not result in unnecessary distress. Specific hypotheses are:

- Primary outcome: For patients with clinically significant symptoms, adequate satisfaction as measured using the 8-item Client Satisfaction Questionnaire (CSQ-8) and as evidenced by mean score of at least 22 points.
- Secondary outcome: For patients with clinically significant symptoms, adequate proportion of clinically significantly improved (12), in accordance with Jacobson and Truax (20). At least 1/3 of participants reporting a reliable reduction in anxiety (on the GAD-7) and a GAD-7 score below cut-off (8p) after the course. At least 1/3 of participants reporting a reliable reduction in depression (on the PHQ-9) and a PHQ-9 score below cut-off (10p) after the course.

Exploratory secondary outcomes also include:

- Adherence to the protocol, operationalised as the number of lectures attended.

[Translated from the original that was approved by the Swedish ethical review authority]

- Self-reported lifestyle behaviours at baseline, and change in lifestyle behaviours. Due to limited power, this focuses on within-group effect sizes and not inferential statistics.
- The proportion of patients in need of additional mental health interventions, as determined by a clinician interviewer after the course.
- The proportion of patients who report a perceived need of additional interventions.
- Adverse events during the intervention

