### ***Description of the research project (methods)***

#### *Design and power*

This study is a within-group trial (i.e., observational study) where 68 patients with common clinically significant psychiatric problems in terms of anxiety and depression are recruited in the primary care system of Stockholm[, Sweden]. The intervention is evaluated in terms of [satisfaction, ]adherence and self-reported symptom outcomes. Power was determined to enable the analysis of data based on a general linear model with dependent means (pre-post) with 80% power in studying effects on symptoms corresponding to  $d=0.45$  given  $\alpha=0.05$  and the expected data loss (no data at post intervention) of 40%. The effect size  $d=0.45$  was chosen on the basis of effects reported by similar interventions in British primary care (12). Up to 25 patients with subclinical symptoms (PHQ-9<10 and GAD-7<8) are also recruited for an exploratory investigation of satisfaction and preliminary efficacy in this patient group.

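### For perceived stress (PSS) and WHODAS 2.0, measured only before and after the course, the plan names no model and no handling of missing post-intervention scores, and leaves the weekly symptom scores unused

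*Combined protocol and SAP*

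**What the plan says.** The questionnaire table under Measurements and psychometric instruments schedules PSS and WHODAS 2.0 at the pre- and post-intervention assessments only. GAD-7 and PHQ-9 are also collected at screening, in each of weeks 1 to 5 and at 3 months.

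Design and power states that "68 patients with common clinically significant psychiatric problems in terms of anxiety and depression are recruited". The number is based on "a general linear model with dependent means (pre-post) with 80% power" and on "the expected data loss (no data at post intervention) of 40" per cent.

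Evaluation and statistical analysis has three relevant sentences:
- A last-observation rule, given only for clinically significant improvement, which concerns GAD-7 and PHQ-9.
- Linear mixed models for dose-response and for change over time, on condition that they suit the data.
- Immediately afterwards, "Linear regression is used for other continuous outcomes".

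None of these names PSS or WHODAS 2.0, and no analysis set or missing-data method is stated for them. Within-group effects are to be given as Cohen's d, and standardised effects compared with the British reference data.

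Research question (study aims) says that perceived stress, functional impairment and adverse events are surveyed, among other purposes, "to assess the relevance of the intervention for stress-related mental health problems" and to allow comparison with other protocols.

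**The concern.** A patient with no post-intervention score on PSS or WHODAS 2.0 has no later value on that scale to stand in for it. The estimated change therefore depends heavily on the model chosen and on how the missing scores are treated, and the plan fixes neither. There is no control arm in which similar dropout might offset the bias.

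If patients who are improving less also tend to stop answering, the reported change on both scales will look better than it was for the clinical group as a whole. That estimate would inform the course's relevance for stress-related problems and its comparison with other protocols. The weekly symptom scores are the best available evidence on how dropouts were doing, yet neither model mentioned in the plan, applied to each scale by itself, would use them.

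**Working it through.** **1. The plan's own figure.** Inputs from Design and power: d = 0.45, alpha = 0.05 (sidedness not stated), power 80%, 40% without post data. A paired t-test with two-sided alpha and the noncentral t distribution needs n = 41 pairs (power 80.3%; 40 pairs give 79.3%). Inflating, 41 / (1 − 0.40) = 68.3, which agrees with 68. The sample size thus already covers the loss of precision. What remains is bias.

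**2. How many patients are affected.** 0.60 × 68 = 40.8, about 41 with post data; 68 − 41 = 27 without. The 40% was set for symptom effects, but it is defined as having no post-intervention data, so it carries over to PSS and WHODAS 2.0.

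**3. What each permitted model does with the 27.**
- Regression of the post score or of the change: they drop out.
- Two-occasion mixed model: they contribute the pre score only. The estimated post mean is (completer post mean) + b × (pre mean of all − pre mean of completers), where b is the completers' regression slope of post on pre.

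**4. Range without a dropout model.** Take d = 0.47, which the background gives for work-related functional impairment in the British data, as the completers' change. Whole-group change = 0.6 × 0.47 + 0.4 × (change in the others). If the others change by 0, this is 0.28; if by 0.47, it is 0.47.

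**5. Dropout that follows the weekly symptom course.** Assumptions not in the documents: log-odds of a missing post score rise by 0.5 or 1.0 per SD less weekly improvement; correlation of scale change with weekly symptom change is 0.4 to 0.7; for the mixed model, pre-post correlation r = 0.5; every dropout has a weekly score. Simulated with n = 68 and 40% missing.

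The mixed-model column can be checked by hand. Adjusting for the pre score removes a share (1 − r)/2 of the completer bias, so (1 + r)/2 = 0.75 of it remains. At r = 0.5 the SD of change, √(2 − 2r) = 1, equals the SD of the score, so both columns are in the same unit.

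| Correlation | Log-odds per SD | Completer overstatement (simulated) | Mixed model (0.75 × completer) |
|---|---|---|---|
| 0.4 | 0.5 | 0.080 | 0.060 |
| 0.4 | 1.0 | 0.136 | 0.102 |
| 0.6 | 0.5 | 0.119 | 0.089 |
| 0.6 | 1.0 | 0.198 | 0.149 |
| 0.7 | 0.5 | 0.131 | 0.098 |
| 0.7 | 1.0 | 0.234 | 0.176 |

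Direct simulation of the mixed model gave 0.06 to 0.18 SD. The completer bias is 0.5 to 1.6 of its standard error. Conditioning on the pre score and weekly symptom change leaves a bias of at most 0.004 SD, with a standard error of 0.14 to 0.16 against 0.15 to 0.16 for completers.

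**6. Other mechanisms.** True change −0.47, pre-post correlation 0.4 to 0.6, same slopes:
- Completely at random: both models recover −0.47.
- Dropout depends on the pre score: completers −0.27 to −0.40 (too small); mixed model −0.47.
- Dropout depends on the unseen post score: completers −0.55 to −0.67; mixed model −0.59 to −0.76. Both are biased, the mixed model more.

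If dropout depends on the scale's own change, completer bias is 0.19 to 0.34 SD, and imputing from weekly symptom change alone still leaves 0.10 to 0.29 SD.

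**The case against.** A reader might infer that PSS and WHODAS 2.0 are to be analysed by linear regression, so that patients without post data cannot enter the analysis and the result is for completers only. The documents do not support this. The regression sentence names neither scale, and the sentence before it assigns change over time to mixed models without limiting them to GAD-7 and PHQ-9. Pre-to-post change fits that description naturally, and a mixed model keeps every patient with a pre score. For the same reason, the plan does not establish that these results would refer to a different patient set from the symptom results.

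Four further objections have force:
- The near-zero bias in step 5 follows partly from the set-up: dropout was made to depend on the variable that is then conditioned on. Step 6 shows how much less is gained otherwise.
- A favourable bias is only one possibility. Dropout related to the pre score makes the completer change too small.
- The documents give no weekly completion rate for patients who lack post data. If only half of them have usable weekly scores, up to about half of the mixed-model bias remains.
- Imputing from all ten weekly scores plus pre scores and attendance is too much for about 41 completers. With 13 predictors the standard error was 0.16 to 0.18, against 0.15 to 0.16 with one.

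It is also fair that these scales carry no hypothesis or success threshold, that the study is a single-arm pilot, and that 68 already allows for 40% loss.

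These objections limit the claim and shape the remedy. They do not answer the gap itself: no model or missing-data rule is stated, and a mixed model on two occasions learns only the pre score from dropouts. Using weekly symptom change was never worse than that mixed model under any mechanism examined. The same cannot be said against the completer analysis when dropout depends on the unseen post score, which is why sensitivity analyses are needed.

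**Conclusion.** The point holds as a cheap improvement. The plan leaves open which model applies to PSS and WHODAS 2.0 and how about 27 of 68 missing post scores are handled, and neither permitted model draws on the weekly GAD-7 and PHQ-9. If dropout follows weekly symptom course, improvement is overstated by about 0.08 to 0.23 SD under a completer regression and 0.06 to 0.18 SD under a two-occasion mixed model. These sizes rest on the assumed slopes and correlations, on a pre-post correlation of 0.5 for the mixed model, and on the 40% loss being realised. The documents do not say which dropout mechanism applies, so neither the direction nor the size is established for this trial. The primary outcome and the GAD-7 and PHQ-9 responder hypotheses are not affected.

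**What to change.** In Evaluation and statistical analysis, name PSS and WHODAS 2.0 and state:
- **Analysis set:** all clinical patients with a pre-intervention score on the scale.
- **Method:** multiple imputation of the post score, or a joint mixed model with the symptom scores, giving pre-to-post change and Cohen's d.
- **Auxiliaries:** the pre score plus a small set, such as the last available or average weekly change in GAD-7 and PHQ-9 and the number of lectures attended, instead of all ten weekly scores.
- **Sensitivity analyses:** the completer result, and a not-at-random analysis that shifts the imputed scores by a range of deltas.
- **Reporting:** how many patients without post data had weekly scores.

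The cost is a few sentences and modest programming; no new data are needed. The main analysis would rely on missing at random given the weekly scores. It removes only part of the bias if dropout depends on the unseen post score or if weekly scores are also missing, and the reported change may be slightly less favourable.
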